**Exploratory Objectives:**

- To examine the tumor-immune microenvironment and the circulating immune cell and inflammatory protein composition in responders vs non-responders.
- To grow tumor organoids from tissue samples collected
- To isolate and characterize circulating tumor cells (CTCs) from peripheral blood

Specifically, will examine:

1. Cytokine levels, including type I interferon (IFN-I)
2. Frequencies of immune cells among peripheral blood mononuclear cells (PBMCs): CD4+ T cells, CD8+ T cells, natural killer (NK) cells, myeloid-derived suppressor cells (MDSCs), T regulatory cells (Tregs), macrophages, dendritic cells (DCs)
3. Frequencies of tumor-infiltrating lymphocytes (TILs) in tumor samples
4. T cell receptor (TCR) repertoire of CD8+ T cells from PBMCs and TILs
5. RNA sequencing profiles of tumors, tumor organoids, and CTCs
6. Mechanisms of resistance using tumor organoids

[figure not shown]
**Endpoints:** Co-Primary Endpoints:

- 12-month Progression-Free Survival
- Safety in terms of Incidence of  $\geq$  Grade 3 Toxicities related to therapy given

Secondary Endpoints:

- 12-month Overall Survival
- Response Rate
- Median Progression-Free Survival
- Median Overall Survival
- Pattern of Disease Progression

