## **2.6 Correlative Studies Background**

### **2.6.1 Tumor-Immune Microenvironment and Circulating Immune Cells/Inflammatory Proteins**

An anti-tumor immune response is dependent on the appropriate balance of activities

from effector cells and suppressor cells in the tumor-immune microenvironment. ICB therapies can alter the compositions of circulating and tumor-infiltrating immune cells and these compositions can correlate with treatment response. Additionally, radiation therapy to tumors causes accumulation of DNA in the cytoplasm of irradiated cells which in turn leads to the activation of the cyclic GMP-AMP synthase (cGAS)/stimulator of interferon genes (STING) pathway, with the resultant production of type 1 interferon (IFN) and other pro-inflammatory cytokines. These cytokines also play a role in tumor-immune response. Other cytokines and soluble factors that can be increased by radiation therapy may be associated with immune suppression (e.g., soluble MICA/B, soluble CD73).

We therefore will plan to examine the tumor-immune microenvironment and the circulating immune cell and inflammatory protein composition in the study subjects, as correlative studies. Specifically, we will isolate peripheral blood mononuclear cells (PBMCs) and examine them for frequencies of CD4+ T cells, CD8+ T cells, natural killer (NK) cells, myeloid-derived suppressor cells (MDSCs), T regulatory cells (Tregs), macrophages, and dendritic cells (DCs). We will specifically examine Ki67+PD-1+ CD8 T cells with an effector-like phenotype (HLA-DR+CD38+Bcl-1low) since they have been shown to be predictive of response in lung cancer patients treated with anti-PD-1 when increased within 4 weeks of treatment start from baseline by two to seven-fold. We will also quantify cytokine levels in the peripheral blood of subjects, particularly type-1 IFN. Additionally, if we are able to obtain sufficient tissue from biopsy samples, we will examine the frequencies of tumor-infiltrating lymphocytes (TILs) in these samples, as well as the T cell receptor (TCR) repertoire of the CD8+ T cells from the TILs and the PBMCs. These studies may provide insight into the mechanisms of immune response and resistance to the treatment modalities used in this study.

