#### **6.1.2.3 Cycle 3 Day 1 (Day 43) (± 7 days)**

- CT Chest and Abdomen/Pelvis with or without Contrast or PET-CT Skull Base to Thigh – should ideally be done with results obtained prior to D43
- MRI Brain with and without Contrast if indicated – should ideally be done with results obtained prior to D43
- Interval Medical History
- Concurrent Medications
- Vital signs including Height and Weight
- Physical Exam
- Labwork: CBC with differential; Serum Chemistry with Liver Function Tests; Amylase and/or Lipase; Thyroid Function Panel; beta-hCG (for pre-menopausal females)
- Adverse Event Evaluation
- Blood for Correlative Studies
- Carboplatin AUC = 5-6 mg/mL per min IV or Cisplatin 75-80mg/m^2 IV on D43
- Etoposide 80-100mg/m^2 IV on D43, D44, and D45
- Durvalumab 1500mg IV on D43

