## 9. Correlative/Special Studies

### 9.1 Tumor-immune microenvironment and the T-cell response

These studies will be done in the laboratory of [name], MD at WCM.

A comprehensive approach is proposed to analyze immunological changes that reflect both local and systemic responses, and general immune activation as well as tumor antigen-specific T cell responses. To this end, serial blood samples (50-ml) will be collected for serum and peripheral blood mononuclear cells (PBMC): at baseline, day 43, day 85 (at response evaluation) and thereafter every 8 weeks and at progression. Small aliquots of PBMC will be used ex vivo for preparation of DNA and RNA, and the remainder preserved frozen until evaluation by flow cytometry and/or by functional assays. Tumor tissue will be obtained at baseline, at day 85 and at progression from patients who consent to optional biopsies. Three 18G cores will be allocated for the following: DNA and RNA isolation (snap frozen), histology and multiplex imaging (fixed in formalin), and for generation of organoids by the EIPM Ex-vivo Lab (see section 9.2.1).

Flow cytometry analysis of circulating PBMC: Cryo-preserved PBMC isolated from serially collected blood following standardized SOPs, will be analyzed by multi-parameter flow cytometry. Specifically, levels of regulatory T cells (Tregs), will be monitored, and T cells (CD3+CD4+ and CD3+CD8+) analyzed for markers of naïve, effector and central memory phenotype (CD45RA/CCR7), proliferation (Ki67), and activation/exhaustion (CD25, CD137, PD-1, Tim-3, CTLA-4, and LAG3). Myeloid cells will be investigated for the expression of granulocytic and monocytic MDSC markers, and for the expression levels of MHC-I and MHC-II molecules, costimulatory and co-inhibitory molecules, including PD-L1. We will measure Ki67+PD-1+ CD8 T cells with an effector-like phenotype (HLA-DR+CD38+Bcl-1low) since they have been shown to be predictive of response in lung cancer patients treated with anti-PD-1 when increased within 4 weeks of treatment start from baseline by two to seven-fold .

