#### **13.2.3 Investigational Agent or Device Risks (Expected Adverse Events)**

As the combination of platinum + etoposide chemotherapy and Durvalumab immunotherapy is now FDA-approved for patients with ES-SCLC, the "investigational

agent" in this study will be the sub-ablative radiation. Mild to moderate (grade <3) adverse events from thoracic radiation include the following: esophagitis, dermatitis, radiation recall reaction, pleural effusion, pericardial effusion, pleuritic pain, non-cardiac chest pain, chest wall pain, pneumonitis, atelectasis, cough, dyspnea, pulmonary fibrosis, generalized muscle weakness, fatigue, photosensitivity, telangiectasias, FEV decrease, WBC decrease, lymphocyte count decrease, and neutrophil count decrease. Severe adverse events (grade ≥3) from radiation may also include the above mentioned plus those listed in Table 6.

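### Circulating immune cells are read as shares of PBMCs during treatment listed as lowering lymphocyte counts, with no absolute count shown beside them, although a CBC differential is scheduled at every correlative draw

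*Combined protocol and SAP*

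**What the plan says.** **Read-out.** Item 2 of the exploratory list, in the Protocol Summary and again in section 1.2.2, is "Frequencies of immune cells among peripheral blood mononuclear cells (PBMCs", followed by CD4, CD8, NK, MDSC, Treg, macrophage and dendritic cells. Section 2.6.1 repeats this: "we will isolate peripheral blood mononuclear cells (PBMCs) and examine them for frequencies of CD4+ T cells, CD8+ T cells".

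**Assay.** Section 9.1 takes blood at baseline, day 43, day 85, every 8 weeks after that, and at progression. Of the assay it says "Cryo-preserved PBMC isolated from serially collected blood following standardized SOPs, will be analyzed by multi-parameter flow cytometry". For Tregs it says "levels of regulatory T cells (Tregs), will be monitored", without a unit or denominator. It gives no denominator for MDSCs either, and no counting step or cells-per-volume unit for any population.

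**Expected effect on the denominator.** Section 13.2.3 includes "WBC decrease, lymphocyte count decrease, and neutrophil count decrease" among the adverse events expected from thoracic radiation.

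**Blood counts.** The visit lists in section 6.1.2 that carry correlative blood (Cycle 1 Day 1, Cycle 3 Day 1, Cycle 5 Day 1 and beyond, End of Treatment) also carry "Labwork: CBC with differential; Serum Chemistry with Liver Function Tests". After day 85 the CBC repeats every 28 days and correlative blood every 8 weeks, so each scheduled draw coincides with a scheduled CBC.

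**Analysis.** Section 12.4 covers the primary and secondary endpoints only. No section brings the CBC into the flow-cytometry read-out.

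**The concern.** Isolated, frozen PBMCs yield proportions. Unless a blood count is brought in, the number of cells per volume of blood is lost. A proportion rises when other cells are lost, stays flat when all cells are lost equally, and falls by less than the count when a population shrinks along with much of the denominator. If the denominator shrinks between baseline and an on-treatment sample, the frequency does not show which of these has happened.

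This matters because section 3.1 describes a single-arm study, so no concurrent group shows how cell composition shifts under chemo-immunotherapy alone. The rationale in section 2.4 is that radiation may strengthen the immune response, and section 3.2 wants data to support a larger randomized trial. A change in share that merely reflects lymphocyte loss could be taken as biological support for that rationale, or a real loss of cells could be missed. What is at stake is the interpretation of on-treatment change, and of on-treatment differences between responders and non-responders.

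**Working it through.** The plan states no figure on this point, so there is nothing to reproduce first. The depth of lymphocyte loss and the baseline cell mix are not in the documents. Every value below is an assumption, shown over a range.

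**1. Monocytic MDSCs, count unchanged.** Assume MDSCs are 5% of PBMCs, lymphocytes are 75%, and lymphocytes fall by a fraction *d*.

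New share = 0.05 / (1 − 0.75*d*)

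| *d* | New share | Apparent change | True change in count |
|---|---|---|---|
| 0.30 | 0.05/0.775 = 6.5% | 1.29-fold | 1.00-fold |
| 0.50 | 0.05/0.625 = 8.0% | 1.60-fold | 1.00-fold |
| 0.70 | 0.05/0.475 = 10.5% | 2.11-fold | 1.00-fold |

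A second assumed mix gives a similar size. Per µL: CD4 800, CD8 400, B 200, NK 200, monocytes 400, MDSC 40; total 2,040. With lymphocytes at 75%, 50% and 30% of baseline, the MDSC share goes from 1.96% to 2.44%, 3.23% and 4.35%, which is 1.24-, 1.65- and 2.22-fold.

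**2. CD8 cells, uniform lymphocyte loss.** Same assumptions as the first mix, with CD8 cells 15% of PBMCs.

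New share = 0.15(1 − *d*) / (1 − 0.75*d*)

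| *d* | New share | Change in share | Change in count |
|---|---|---|---|
| 0.30 | 0.105/0.775 = 13.5% | 0.90-fold | 0.70-fold |
| 0.50 | 0.075/0.625 = 12.0% | 0.80-fold | 0.50-fold |
| 0.70 | 0.045/0.475 = 9.5% | 0.63-fold | 0.30-fold |

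The share moves in the right direction but understates the loss. If every PBMC type halved, all shares would stay at 1.00-fold while all counts halved.

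**3. CD8 cells, uneven loss.** Take the second mix and let CD4 fall to 50%, CD8 to 80%, B to 20%, NK to 60% and monocytes to 75%, with MDSC unchanged. The new total is 400 + 320 + 40 + 120 + 300 + 40 = 1,220.

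- Share: 400/2,040 = 19.6% before, 320/1,220 = 26.2% after, which is 1.34-fold.
- Count: 320/400 = 0.80-fold.

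Share and count point in opposite directions.

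**4. What a count adds.** Absolute count = PBMC fraction × (lymphocytes + monocytes per µL). In step 3, assuming the analyser counts the MDSCs as monocytes, unrounded fractions give (400/2,040) × 2,040 = 400 before and (320/1,220) × 1,220 = 320 after. The fall to 0.80-fold is recovered. In step 1 the count stays at 1.00-fold throughout.

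**The case against.** The strongest case on the other side has five parts.

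- **Section 9.1 does not itself say share of PBMCs.** It speaks of levels of Tregs and marker expression, and it does not name NK cells. This is right. The share wording is in exploratory item 2 and section 2.6.1; section 9.1 leaves the denominator open. Much of its T-cell panel is phenotype within T cells, for which percent of parent is the natural unit.
- **The evidence for a moving denominator is thin.** Neutrophils are not mononuclear cells, so the neutropenia in Appendix A does not bear on it. Leucopenia (15%, any grade, in the durvalumab arm) does not say which cells fell, and no Appendix A table lists lymphopenia, although those tables apply incidence thresholds or cover selected event types. What remains is one item in section 13.2.3, without rate or depth. Last etoposide is on day 66, so draws from about day 141 are on durvalumab alone. This stands as a limit on size, not on the principle.
- **T-cell shares need not rise.** A reader might infer that the plan will generally show false T-cell expansion. Wholly spared CD8 cells at 15% of PBMCs, with all other PBMCs down 30%, 50% or 70%, would give 0.15/0.745, 0.15/0.575 and 0.15/0.405, or 1.34-, 1.74- and 2.47-fold. Nothing in the documents supports complete sparing, and uniform lymphocyte loss moves the share down.
- **Not every responder contrast is exposed.** The Cycle 1 Day 1 sample precedes treatment, so a baseline comparison is untouched. That responders and non-responders differ in depth of cytopenia is possible but not shown.
- **The consequence is reversible.** No test or decision hangs on this read-out, no section says a rise in frequency will be called expansion, and the CBC data will exist anyway. This is true and keeps the point modest. It does not remove the case for showing the count.

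**Conclusion.** The point holds in a limited form. For change from baseline on treatment, and for on-treatment responder contrasts, frequencies among PBMCs alone cannot separate a change in cell number from a change in the other cells, and the plan brings in no count. Under the assumed 30% to 70% lymphocyte loss, an unchanged monocytic MDSC count appears to rise about 1.3- to 2.1-fold. For CD8 cells the share can fall by less than the count, or rise while the count falls, depending on which cells are lost. These sizes rest wholly on assumed cell mixes and loss.

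The documents do not support reading this as a prediction that T-cell expansion will be falsely reported, as a flaw in the pre-treatment contrast, or as a threat to 12-month PFS or the safety endpoint. Nor do they require the absolute count to replace the frequency, since relative composition is a legitimate quantity. This is a worthwhile, inexpensive improvement to an exploratory objective.

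**What to change.** In section 9.1:

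1. State the denominator for each population, including Tregs, MDSCs and Ki67+PD-1+ CD8 cells.
2. For lineage populations, report absolute cells/µL = PBMC fraction × (lymphocytes + monocytes), using the CBC differential of the same scheduled visit. Show it beside the frequency for change from baseline and for on-treatment comparisons of responders and non-responders.
3. Describe a change as expansion or loss of cells only with the absolute count shown.
4. Keep percent of parent for phenotype markers such as Ki67+PD-1+ within CD8. The one fold-change signal that section 9.1 cites, "when increased within 4 weeks of treatment start from baseline by two to seven-fold", is therefore left in that form, with its denominator stated.

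**Cost.** One derived variable from data already scheduled, and no new sample. The count carries CBC measurement error. After day 85 the CBC and the correlative blood each have their own ±7-day window, so both dates should be recorded when they are paired. The formula does not suit granulocytic MDSCs, which should stay as a frequency or have a separate denominator.

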## 9.2 Organoids from SCLC Tissue

Tissue from standard of care or research biopsies will be brought to the EIPM via standard operating procedures in place here at WCM. Organoid specimens are biobanked when the culture has demonstrated that it can be successfully expanded beyond its initial plating. We define successful establishment of PDTO cultures as when they contain viable cells that form spheroid-like structures and can be propagated after the initial processing for at least five passages. Tumor verification assays involve histologic examination to ensure that the tissue initially submitted is tumor, and that the growing organoids are tumoral as well. The specimens are then characterized, stored in our living biobank, and used for functional studies. Once they are considered successfully established, they are subjected to Whole-Exome Sequencing (WES) to test concordance at base-pair resolution with the native tumor. We evaluate tumor purity and ploidy using the CLONET computational framework (CLONAlity Estimate in Tumors).

Our plan is to optimize and use the Operetta system (see background section 2.5.3) to run the high throughput drug screening planned in the current study. Drug screenings performed in our high throughput platform would have two readouts: a primary readout of organoid growth/death as determined by imaging over time and a secondary endpoint readout of cell metabolism as an indirect measure of cell viability. 3D analysis includes parameters such as intensity, position, morphology (such as solid vs. hollow sphere, cell shape, etc.) and texture. Following 3D analysis, a final endpoint luminescence measurement using Cell titer Glo will be taken to measure cell viability on our high

throughput drug screening robot's Biotek Synergy Neo plate reader. Each compound will be tested in a dose-response manner and hits will be determined based on two primary criteria, efficacy of each compound relative to the rest of the compounds in the screen (AUC), and impact of each compound on that specific organoid relative to the rest of the organoids that have been tested (Z-score).

### **9.3 Circulating Tumor Cells**

These studies will be done in the laboratory of [name], PhD at WCM.

All subjects in this study will get blood samples drawn for circulating tumor cell (CTC) enrichment. CTCs and PBMCs will be collected before the initiation of therapy (baseline), during the course of the treatment (on-treatment) and at the moment of disease progression (relapse).

Twenty mL of peripheral whole blood will be collected at each time point in two 10 mL EDTA tubes (purple top) by standard venous phlebotomy. Gently invert the tubes 8-10 times after blood collection. Tubes will be stored at ambient temperature until brought to the [name] lab at Weill Cornell Medicine. Do not freeze the tubes. The tubes must be received by the [name] lab within 24 hours of collection. Ensure that the EDTA tubes are transported at ambient temperature. If collected samples cannot be transported on the same day of collection (e.g. Friday-Saturday or Holiday collections), please contact the [name] lab at [contact] for further instruction at least 24 hours prior to anticipated collection.

CTC enrichment will be performed at the [name] lab and CTCs will be analyzed for transcriptomic studies. Briefly, CTCs will be enriched by negative depletion using the RosetteSep Human CD45 depletion cocktail (STEMCELL technologies). If SCLC CTCs are found to express TfR, then this protein will also be used as a positive selection marker. At each time point, 1 mL of the blood collected will be used to isolate peripheral blood mononuclear cells (PBMCs), using density centrifugation (Ficoll).

RNA will be extracted from CTCs and PBMCs and gene expression will be analyzed by RNA-sequencing. Differentially expressed genes in the enriched CTCs and matching PBMCs between C1D1 and subsequent time points will be identified, and gene set enrichment analysis of differentially expressed genes between C1D1 and the on-treatment and relapse time points will be performed to identify specific pathways and biological functions associated with sensitivity or resistance to the treatment.

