As a correlative study of this trial, we will prospectively and longitudinally isolate and molecularly analyze CTCs and matching peripheral blood mononuclear cells (PBMCs) from subjects receiving the combination of chemo-immunotherapy and non-ablative radiation. The goal of our analysis is to identify genes/pathways associated with clinical response/resistance to this treatment by performing untargeted RNA sequencing of patient-derived-CTCs (tumor compartment) with matching PBMCs (immune compartment).

To overcome the limitations intrinsic to an EpCAM-based positive selection, we will enrich CTCs by using the antigen-agnostic RosetteSep™ Circulating Epithelial Tumor Cells

enrichment assay (STEMCELL™ Technologies); this approach utilizes anti-CD45/antiglycophorin A antibody complexes that crosslinks red blood cells (glycophorin A+) and white blood cells (CD45+), which are subsequently eliminated by gradient-based separation. Such antigen agnostic approach allows the enrichment of a pool of heterogeneous subpopulation of CTCs compared to traditional approaches that rely on positive selection of epithelial markers (i.e. EpCAM). Additionally, if work in the lab shows that SCLC CTCs express TfR (as NSCLC CTCs do), then we will also attempt to use this marker to help isolate CTCs from the subjects in this study.

Gene set enrichment analysis of differentially expressed genes between baseline, on-treatment, and relapse CTCs will be performed to identify pathways associated with onset of resistance to the treatment. To assess immune cell activation induced by treatment, matched PBMCs will be isolated from the above and gene expression analysis will be performed. Gene set enrichment analysis of differentially expressed genes between baseline and on treatment will reveal immune signatures characterizing host immune activation as a consequence of the treatment and will identify immune components that discriminate responders from non-responder patients.

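### The CTC and PBMC RNA-sequencing contrasts compare time points only, so they cannot by themselves support the sensitivity and responder-discrimination claims attached to them

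*Combined protocol and SAP*

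**What the plan says.** Section 9.3 sets out the differential expression step: "Differentially expressed genes in the enriched CTCs and matching PBMCs between C1D1 and subsequent time points will be identified". Enrichment follows on the same axis: "gene set enrichment analysis of differentially expressed genes between C1D1 and the on-treatment and relapse time points will be performed to identify specific pathways", and these pathways are to be read as "associated with sensitivity or resistance to the treatment".

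Section 2.6.3 states the purpose: "The goal of our analysis is to identify genes/pathways associated with clinical response/resistance to this treatment". Its CTC analysis is also by time point, but covers all three: "Gene set enrichment analysis of differentially expressed genes between baseline, on-treatment, and relapse CTCs will be performed", with onset of resistance as the target. For PBMCs it says "Gene set enrichment analysis of differentially expressed genes between baseline and on treatment will reveal immune signatures" of host immune activation, and that the same analysis "will identify immune components that discriminate responders from non-responder patients".

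The Exploratory Objectives in the Protocol Summary name a comparison by response, "composition in responders vs non-responders", for the tumor-immune microenvironment and the circulating immune cells and proteins. The CTC objective is a separate bullet without that comparison. Section 12.4 covers primary and secondary endpoints only, and section 9.1 describes assays. No section gives a responder contrast, a grouping rule or multiplicity control for the RNA-sequencing data.

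**The concern.** The contrast and the claim address different hypotheses. A comparison of C1D1 with a later sample tests whether mean expression changes over time. A claim about sensitivity, or about separating responders from non-responders, needs a test of whether the change (or the C1D1 level) differs by response.

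All subjects are planned to receive platinum, etoposide, durvalumab and radiation, and there is no concurrent control. A gene that shifts equally in responders and non-responders shows up in the time contrast while saying nothing about response. If the test pools all subjects, a gene that moves in opposite directions in the two groups can average out and be missed.

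At stake is the meaning of the signatures this correlative study produces. Section 3.2 says the trial should provide data to support a larger randomized trial, so a pathway labelled as response-related on this evidence could misdirect later work.

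**Working it through.** **Stated figure.** The documents give no sample size, power, alpha or FDR for this analysis, so there is no figure to reproduce.

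**Contrast against claim.**
- 9.3, CTCs and PBMCs: C1D1 versus later samples, read as sensitivity or resistance. The contrast has no response term.
- 2.6.3, PBMCs: baseline versus on-treatment, read as treatment-induced immune activation (which it can show) and as discriminating responders (which it cannot).
- 2.6.3, CTCs: baseline, on-treatment and relapse, read as onset of resistance. Section 9.3 places the relapse sample at disease progression, so the contrast bears on acquired resistance. It still mixes resistance with accumulated treatment exposure and has no non-progressing comparator at a matched time.

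**Inputs for an illustration.** From the documents: 34 evaluable subjects (section 12.2), which is the number for the primary endpoints and not a count of paired RNA samples. Assumed: 34 or 20 complete pairs, 50-80% responders, normal within-subject changes with SD 1, and one pooled paired t-test as the time contrast (the protocol names no test).

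**Step 1: the same change in everyone, unrelated to response.** The pooled test has noncentrality √n × δ. With n = 34 and δ = 0.5 this is 5.831 × 0.5 = 2.92, against a critical t of 2.03 on 33 df. The comparison of change by response has noncentrality 0, so it rejects at its nominal 5%.

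| Pairs | Common change (SD) | Time contrast, p<0.05 | Change by response, p<0.05 |
|---|---|---|---|
| 34 | 0.5 | 81% | 5% |
| 34 | 0.8 | 99% | 5% |
| 34 | 1.0 | >99% | 5% |
| 20 | 0.5 | 56% | 5% |
| 20 | 0.8 | 92% | 5% |
| 20 | 1.0 | 99% | 5% |

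The time-contrast column is ordinary power against a real change over time. It becomes an error only when the gene is then called response-related.

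**Step 2: a true 1.25-SD difference in change by response, with mean change zero overall, 34 pairs.** The two-sample noncentrality is 1.25 × √(n₁n₂/(n₁+n₂)), with a critical t of 2.04 on 32 df.

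| Responders/non-responders | Noncentrality | Change by response | Pooled time contrast |
|---|---|---|---|
| 17/17 | 3.64 | 94% | 2% |
| 22/12 | 3.48 | 92% | 2% |
| 27/7 | 2.95 | 81-82% | 3% |

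If only the 7 non-responders change, by 1.25 SD, the pooled contrast finds the gene 23% of the time and the response contrast about 81%. If only the 27 responders change, by 1.0 SD, the order reverses: 99% against 63%.

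**Step 3: the response contrast after multiplicity control.** The step 2 powers are per gene at an unadjusted 0.05. With 10,000 genes, Benjamini-Hochberg at 5% and a 1.25-SD difference in the linked genes, 100 simulated data sets per setting give:

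| Split | 100 linked genes | 500 linked genes |
|---|---|---|
| 17/17 | about 30% | about 58% |
| 22/12 | about 23% | about 50% |
| 27/7 | about 6% | about 22% |
| 31/3 | below 1% | below 1% |

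At 31/3 the unadjusted per-gene power is 52%.

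**The case against.** The strongest reply is that the intent to use response is already written. The Exploratory Objectives name responders and non-responders (section 1.2.2 speaks of responding and resistant individuals). The list of specific measurements after those bullets includes RNA sequencing profiles of CTCs, and 2.6.3 mentions discrimination by response. No section prescribes a single pooled test. This stands in part. A reader might infer that response plays no role in the plan, and the documents do not support that. What is missing is the contrast that would carry the intent out.

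Three other strong readings also go too far.
- A reader might conclude that changes common to all subjects will be reported as response signatures. That is a forecast. No section says every time-changing gene will be so labelled, and 2.6.3 separately describes the PBMC contrast as treatment-induced activation.
- A reader might treat the resistance claim as equally unsupported. Relapse samples come from progressing subjects and do carry information on acquired resistance.
- A reader might say that on-treatment versus relapse is absent from the plan. The three-way CTC comparison in 2.6.3 covers it, and only 9.3 is narrower.

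It is also fair to say that the simulated sizes rest on assumed inputs, and that a CR/PR grouping is only one option. Section 2.1 describes high response rates that are mostly not durable, so CR/PR could leave few non-responders and miss durability. Both points stand and shape the fix.

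**Conclusion.** The point holds in limited form. Sections 9.3 and 2.6.3 name concrete between-time contrasts and attach to them a meaning about sensitivity and responder discrimination that such contrasts cannot carry in a single-arm trial. For acquired resistance the support is partial.

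This follows from the text and does not depend on the simulation. The simulation shows only that the distinction can be large: 56% to over 99% flagging of shared changes against 5%, given 20 or 34 pairs and changes of 0.5-1.0 SD, all assumed. A correct response contrast would itself be weak after FDR control, at about 6-30% power with 100 linked genes among 10,000 for splits from 27/7 to 17/17.

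The analysis is exploratory. Primary and secondary conclusions, the safety rules and the sample size are untouched. The text should be corrected before the RNA-sequencing data are analyzed.

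**What to change.** In sections 9.3 and 2.6.3:
1. Keep the C1D1-versus-later contrasts, and describe them as changes on treatment.
2. Base sensitivity and responder claims on a per-gene model with subject as the blocking factor, time point, and time by response. Add a comparison of responders with non-responders at C1D1. Control the FDR, and run gene set enrichment on genes ranked by these response terms.
3. Fix the response grouping in advance: for example RECIST 1.1 CR/PR versus not (already assessed under section 10.3), or a PFS-based grouping if few non-responders are expected.
4. Bring 9.3 into line with 2.6.3 by naming on-treatment versus relapse CTCs for onset of resistance, and state that treatment exposure is a confounder.
5. Label the response findings hypothesis-generating.

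The cost is wording and one added model term, plus the C1D1 comparison. Response status and the samples are already to be collected. The downside is that fewer genes will be reported as response-related, because the response contrast has low power after FDR control, especially with few non-responders. It is also weaker than the time contrast when only a responder majority changes (63% against 99% at 27/7 and 1.0 SD, unadjusted). The on-treatment changes remain available under their own label.
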